Vitamin D toxicity or hypervitaminosis D is characterized by elevated serum calcium levels or hypercalcemia (14). Due to the hypercalcemia, acute symptoms of toxicity can include muscle weakness, confusion, vomiting, anorexia, polyuria and polydipsia. In addition, hypercalcemia can be chronic, and those symptoms of intoxication from hypervitaminosis D could include bone demineralization, pain, and nephrocalcinosis.

Therefore, we believe STOSS therapy will efficaciously, safely and feasibly increase vitamin D levels to above 30 ng/mL in our pediatric CF population. We hypothesize that STOSS therapy

Date: December 20, 2016

Principal Investigator: [name]

Application Number: IRB00081746 (IND # 128487 – IND Sponsor: [name])

administered once in clinic as witnessed by a designated clinician, will maintain 25OHD levels greater than or equal to 30 ng/mL without instances of hypercalcemia (7).

4. Study Procedures

The study is a phase 2 single arm study that will assess the safety, feasibility and efficacy of a high dose of vitamin D3 as cholecalciferol in Cystic Fibrosis pediatric patients with a 25OHD level <30 ng/mL. The members of the study team will enroll 30 participants who have consented and meet eligibility criteria, including a baseline 25OHD level <30 ng/mL which is measured annually, at a minimum, as a part of the current standard of care. All patients with CF, will be consented to participate upon having his/her annual lab work collected.

As patients present with a 25OHD level < 30 ng/mL they will be screened to see if they meet full eligibility criteria for enrollment. This will include a phosphorus level and spot urine calcium to creatinine ratio which will be collected at their CF visit (patients seen at the St. Petersburg office) or within 2 weeks prior to their visit if in Sarasota or Tampa. (See section 5 for complete inclusion/exclusion criteria). Screening will also consist of a urine pregnancy test to be completed the day of the administration of the high dose of vitamin D.

After a patient meets full eligibility criteria, they will be enrolled in the study and we will administer the 250,000 IU vitamin D3 at that visit. Upon administration, each participant will be provided with an oral, one-time dosage of vitamin D3 (cholecalciferol) in the form of capsules that will be swallowed; the capsule cannot be crushed or dissolved in anything in order to be administered.

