The following safety measures have been reviewed and approved by two Johns Hopkins All Children's Hospital Endocrinologists: As additional measures of safety at 7 days to the next working business day of the administration of the 250,000 IU of vitamin D3, all participants will also have a serum calcium and serum phosphorus level measured. If any participant has a serum calcium above the upper limits of normal (ULN) for their age (appendix B), they will be contacted via telephone to be queried about symptoms of hypercalcemia such as muscle weakness, confusion, vomiting, anorexia, confusion, polyuria and polydipsia. If the patient has more than 1 symptom of hypercalcemia and an elevated serum calcium level, we will consider this an adverse event. During this communication, it will be decided if any type of treatment will be needed to remedy the complaint (see section on treatment of hypervitaminosis D from hypercalcemia).

If any participant has a serum calcium level greater than the ULN for age or a serum phosphorus level greater than the ULN for age, a second tier of safety measures will be taken. This will include measuring a PTH with reflex calcium level as soon as possible, within approximately 7 days (± 3 days) of the serum calcium or phosphorus lab draw. In addition, we will obtain a spot urine calcium to creatinine ratio. Calcium levels and/or phosphorus levels will be repeated every 2 weeks (+7 days) until normalized for age. If the spot urine calcium to creatinine ratio is $> ULN$ for age (Appendix C) we will obtain an Endocrinology consult and if symptomatic be instructed to go to the Johns Hopkins All Children's Hospital for evaluation. The urine calcium to creatinine ratio will be repeated in 1 week (+3 days) and then monthly (+7 days) until normalized for age. Proposed treatment for hyperphosphatemia will involve increased fluids and restriction of phosphorus loaded foods. Proposed treatment for hypercalcemia, as reflected by a serum calcium level, is detailed in another section of this protocol.

To evaluate for feasibility, at 7 days to the next working business day after administration of the 250,000 IU administration of Vitamin D3, participants will be contacted by a member of the study team via phone to answer a 10-item questionnaire which is included as an appendix at the end of this protocol. This questionnaire is to assess feasibility of the 250,000 IU Vitamin D3.

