Regardless of serum calcium level or other labs collected, if a participant does become ill after taking the high dose of vitamin D3 (e.g., muscle weakness, confusion, vomiting, anorexia, polyuria and polydipsia, etc.) they will be asked to call the CF office number, [contact]. During this communication, it will be decided if any type of treatment will be needed to remedy the complaint (see section on treatment of hypervitaminosis D from hypercalcemia). If their serum calcium level was within normal limits for age, but they have symptoms of those found with hypercalcemia, it will be noted in our study findings but not classified as an adverse event.

At 12 weeks (± 30 days) from the initial study visit, participants will be required to have another 25OHD level measured via venipuncture as a part of standard of care. In addition, as a part of the

Date: December 20, 2016

Principal Investigator: [name]

Application Number: IRB00081746 (IND # 128487 – IND Sponsor: [name])

first tier of safety measures, a serum calcium and serum phosphorus level will be measured again. If either of these levels is elevated, a PTH level will be measured as soon as possible within approximately 14 days (\pm 3 days) of this serum calcium lab draw. If serum calcium level is above ULN a spot urine calcium to creatinine ratio will be ordered. At 26 weeks (\pm 30 days) and 52 weeks (\pm 30 days) the participants will have 25OHD levels measured again. No additional one-time high dosage of vitamin D3 will be prescribed or provided during the study period for any reason to any of the participants. No additional measures of safety, in the forms of serum calcium labs, serum phosphorus, or PTH will be measured.

Any participant with an elevated serum calcium level of anything above normal limits for age will be instructed to limit calcium containing foods in their diet, stop supplements with additional vitamin D and/or calcium. Since these participants will be called regarding their elevated serum calcium level to query about symptoms of hypercalcemia, we will be able to instruct them on this.

If at any time after the study intervention has started and the participant has a 25OHD level less than 30 ng/mL, they will be placed on the current standard CF Foundation step-wise guidelines for treatment appropriate for their low vitamin D level.

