Appendix A – Phone Survey 1 – week following dosage

NOTE: the following questions will be based on the previous week only and will be about how you usually feel or symptoms you otherwise usually have.

- 1) Over the last week, since you have taken the vitamin D3 of 250,000 IU have you:
 - i) Experienced feeling an increased amount of nausea?
 - (1) NO
 - (2) YES
 - ii) Experienced an increased frequency of emesis (vomiting)?
 - (1) NO
 - (2) YES
 - iii) Experienced an increased amount of diarrhea?
 - (1) NO
 - (2) YES
 - iv) Experienced any constipation?
 - (1) NO
 - (2) YES
 - v) Experienced increased gas production, such as burping or passing gas?
 - (1) NO
 - (2) YES
 - vi) Experienced an increased amount of abdominal pain/stomach aches?
 - (1) NO
 - (2) YES
- 2) Since taking the vitamin D3 last week, have you experienced an increase in heart burn or reflux?
 - i) NO
 - ii) YES
- 3) Did you find the one-time dose of vitamin D3 to be easy to take?
 - i) NO
 - ii) YES

Date: December 20, 2016

Principal Investigator: [name]

Application Number: IRB00081746 (IND # 128487 – IND Sponsor: [name])

- 4) Would this type of medication be something you would do next year if you had another low vitamin D level?
- i) NO
 - ii) YES
- 5) Would you prefer taking a one-time dose of vitamin D to treat a low vitamin D level instead of taking a daily vitamin D supplement?
- i) NO
 - ii) YES

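### No specified item asks participants with normal calcium about five of the six named hypercalcemia symptoms, so symptom frequencies are ascertained differently by calcium result

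*Combined protocol and SAP*

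**What the plan says.** The directed symptom query in section 4 (Study Procedures) has a laboratory trigger, a serum calcium higher than the age-specific limit in Appendix B. For those participants the text states that "they will be contacted via telephone to be queried about symptoms of hypercalcemia such as muscle weakness, confusion, vomiting, anorexia, confusion, polyuria and polydipsia". Later text in section 4, and the risk-minimization steps in section 10, repeat the calcium trigger. Section 3 gives the same symptoms as the signs of toxicity: "acute symptoms of toxicity can include muscle weakness, confusion, vomiting, anorexia, polyuria and polydipsia".

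Separately, about seven days after the dose, all "participants will be contacted by a member of the study team via phone to answer a 10-item questionnaire". Its stated purpose is not safety: "This questionnaire is to assess feasibility of the 250,000 IU Vitamin D3". From the toxicity list, Appendix A contains only the item "Experienced an increased frequency of emesis (vomiting)".

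Participants with normal calcium have two other routes:
- Anyone who becomes ill, whatever the calcium result, is covered by the instruction that "they will be asked to call the CF office number". The same six symptoms are given there as examples.
- The study calendar marks an adverse event assessment for everyone at baseline and at weeks 1, 12, 26 and 52. The calendar footnote and section 8 have all adverse events monitored to 30 days after dosing.

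Section 4 counts raised calcium with more than one symptom as an adverse event. Symptoms with a normal calcium are to be noted but not classified as one. The calendar footnote defines adverse events by 21CFR312.32.

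**The concern.** Safety is the primary objective. Section 9 names the frequency and severity of adverse events among the safety variables and plans to report them as counts and percentages. The study has one arm and no placebo, so participants with normal calcium are the only internal reference for how often these symptoms occur after the dose.

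Under the stated procedures, one group is prompted symptom by symptom, in a call made because the calcium is raised. The other group is prompted for vomiting and otherwise depends on unprompted report or on an assessment without a listed content. A higher symptom count in the raised-calcium group could reflect the prompting, or knowledge of the result, rather than the calcium itself. A child with several of these symptoms but a normal calcium at the draw could go unrecorded.

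**Working it through.** **1. The survey's own count.** Appendix A has question 1 parts i to vi (6 items) and questions 2 to 5 (4 items): 6 + 4 = 10. This matches the 10 items stated in section 4, so no item was lost from the text. Seven of the ten are symptom items (question 1 parts i to vi, and question 2). The other three concern acceptability.

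**2. The toxicity list.** The section 4 query has 7 entries, with confusion given twice, so 6 are distinct. Section 3 names the same 6.

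**3. Side by side.**

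| Symptom | Query after raised calcium | Week-1 survey of all |
|---|---|---|
| Muscle weakness | yes | no |
| Confusion | yes | no |
| Vomiting | yes | yes |
| Anorexia | yes | no |
| Polyuria | yes | no |
| Polydipsia | yes | no |

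The overlap is 1 of 6. Absent from the survey: 6 − 1 = 5, and 5/6 = 83%. The remaining survey symptoms (nausea, diarrhea, constipation, gas, abdominal pain, heartburn or reflux) are not on the list. With one listed symptom, the survey alone can never show more than one.

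**4. How many participants this concerns.** Section 12 budgets second-tier urine testing for 10% of 30 = 3 participants. If no more than 3 have raised calcium, at least 30 − 3 = 27 of 30 are not asked about the five symptoms by any specified item. The 3 is a budget and hold figure, not an expected rate.

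**5. Illustration of under-recording (assumptions, not document figures).** Let k of 30 participants have raised calcium and be fully queried. Let every participant have the same probability q of more than one listed symptom. Let s be the probability that the call-in route or the general assessment records it when calcium is normal.

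Expected true cases are 30q, and expected recorded cases are kq + (30 − k)qs. The unrecorded share is (30 − k)(1 − s)/30, and q cancels.

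| s | k = 1 | k = 3 |
|---|---|---|
| 0.25 | 29 × 0.75/30 = 72.5% | 27 × 0.75/30 = 67.5% |
| 0.50 | 29 × 0.50/30 = 48.3% | 27 × 0.50/30 = 45.0% |
| 0.75 | 29 × 0.25/30 = 24.2% | 27 × 0.25/30 = 22.5% |

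The result is governed by s, on which the documents give no information.

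**6. Classification.** Section 4 keeps symptoms with normal calcium out of the adverse event count. The calendar footnote and section 8 monitor all adverse events to day 30, and the footnote cites the regulatory definition. As written, both the solicitation and the classification of a symptom depend on the calcium result.

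**The case against.** The strongest reply is that the plan already looks for symptoms in everyone. The calendar schedules an adverse event assessment at every main time-point and a hypercalcemia monitoring row at weeks 1 and 12. All adverse events are monitored to day 30, and the call-in instruction names the same symptoms. This stands against one tempting inference, that a symptomatic child with normal calcium would be found only if the family telephones. The documents do not support that. They do not show equal ascertainment either, because call-in is passive and neither calendar row has a stated symptom content.

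A reader might also infer that the adverse event rule compares prompted with unprompted reports. It does not. It defines a composite of raised calcium and more than one symptom, and everyone found raised at a scheduled draw is queried, so that composite is not undercounted there. Section 9 plans no symptom comparison by calcium status.

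Third, better collection would not show whether symptoms accompany raised calcium. With about 3 raised against 27, one arm and no power calculation, that is correct, and the gain should not be described in those terms.

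Finally, the symptom lists are illustrative, so 83% counts items and not missed cases. That also stands.

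On constipation, the item "Experienced any constipation" is worded differently from the other symptom items, which ask about an increase. One might infer that pre-existing constipation becomes a post-dose adverse event, but nothing says that survey answers are counted as adverse events. The survey's introductory note also refers to usual symptoms. It is a wording inconsistency only.

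**Conclusion.** The concern holds in a limited form. Five of the six named symptoms are put to participants by a specified item only after a raised calcium is known, and those participants know the result. Symptom frequencies by calcium status would therefore not be comparable, and symptomatic children with a normal calcium at the draw may be missed. The number missed cannot be derived from the documents. The illustration spans roughly 22% to 72% of those with more than one symptom, depending almost wholly on an assumed capture probability of 0.25 to 0.75.

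A reader might go further and infer that the main safety result is biased. It is not: the primary endpoint is week-1 serum calcium, a laboratory value measured in all participants. The effect is confined to the descriptive symptom and adverse event summaries. The change is worth making because it is cheap and safety is the primary objective. The conclusion assumes that the general adverse event assessment has no symptom checklist outside these documents; if one covers the six symptoms, it should be cited and most of the point falls away.

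**What to change.** - Add five yes/no items to the Appendix A symptom block, each asking about an increase since the dose: muscle weakness, confusion, loss of appetite, increased urination and increased thirst. Coverage of the list on the common call rises from 1 of 6 to 6 of 6.
- Ask the block of all participants on the existing week-1 call, before the calcium result is disclosed where possible. Section 4 gives the draw and the call the same timing, so this is practicable.
- Use the same items on the raised-calcium call and at the week-12 adverse event assessment already scheduled.
- Report the symptoms descriptively by calcium status, with no claim of association.
- Reconcile the section 4 statement that symptoms with normal calcium are not adverse events with the calendar footnote and section 8. Otherwise the added answers will be summarized inconsistently.
- As a minor edit, word the constipation item as an increase, like the other symptom items.

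The cost is five short questions on an existing call and form, a slightly longer conversation, and more reports of background symptoms, which the single-arm design cannot separate from effects of the dose.

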There will not be a placebo group, as the study design does not support this; providing a placebo is not ethical in this population for this condition.

If a patient does not complete the study for any reason, meaning they do not get each set of lab work completed, their results up to that point in time will still be used in the study but their duration of participation will be noted in the results section. Every effort will be made to contact patients who are lost to follow up to ascertain the reason for withdrawal.

Date: December 20, 2016

Principal Investigator: [name]

Application Number: IRB00081746 (IND # 128487 – IND Sponsor: [name])

| Study Procedures | Study Time-points | | | | | | | |
|---|---------------------------|---------------|---------------------|---|------------------------------|--|---------------------------|------------------------|
| | Screening/ Eligibility | Base- line | Week 1 +/- 3 day | Week 1 B.*** Week 1+/- 14 days | Week 12 +/- 30 days | Week 12 B.*** Week 12 +/- 42 days | Week 26 +/- 30 days | Week 52 +/- 30 days |
| Informed Consent | X | | | | | | | |
| 25OHD Lab | X | | | | X | | X | X |
| Screening / Eligibility Verification (including pregnancy test) | X | | | | | | | |
| Eligibility screening: Spot Urine Calcium to Creatinine Ratio | X | | | | | | | |
| Study Registration | | X | | | | | | |
| Medication Review* | | X | | | X | | X | X |
| STOSS Vitamin D3 Administration | | X | | | | | | |
| Serum Calcium Test & Hypercalcemia Monitoring | | | X | X | X | X | | |
| Serum Phosphorus | X | | X | X | X | X | | |
| Parathyroid Hormone (PTH) Level (2 nd tier only) | | | | X | | X | | |
| Spot Urine Calcium to Creatinine Ratio (2 nd tier only) | | | | X | | X | | |
| Administration of Appendix A Questionnaire | | | X | | | | | |
| Adverse Event Assessment** | | X | X | X | X | X | X | X |

* Medication review will consist of surveying the patient's current daily maintenance dosage for vitamin D as previously prescribed.

** AEs and SAEs are defined per 21CFR312.32. All adverse events will be monitored and processed from study start until 30 days after study product administration. All adverse events deemed related to known vitamin D supplementation risks and/or study procedures will be monitored for 12 months post drug administration.

Date: December 20, 2016

Principal Investigator: [name]

Application Number: IRB00081746 (IND # 128487 – IND Sponsor: [name])

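### Section 4 takes hypercalcemia-type symptoms with a normal calcium out of the adverse events, the calendar footnote states no such exception, and Section 9 does not say which rule feeds the AE summary

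*Combined protocol and SAP*

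**What the plan says.** Section 4 contains two classification sentences that depend on serum calcium.

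- **Raised calcium at week 1.** The child's family is telephoned and asked about symptoms, and the rule is: "If the patient has more than 1 symptom of hypercalcemia and an elevated serum calcium level, we will consider this an adverse event".
- **Normal calcium.** For a child who becomes ill after the dose and whose calcium was within limits for age, the rule is that if "they have symptoms of those found with hypercalcemia, it will be noted in our study findings but not classified as an adverse event".

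Sections 3 and 4 name the same symptoms: muscle weakness, confusion, vomiting, anorexia, polyuria and polydipsia.

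The footnote to the study calendar, also in Section 4, gives a general definition: "AEs and SAEs are defined per 21CFR312.32". It states no exception. The footnote and Section 8 both say that every AE is processed until 30 days after dosing, and that AEs related to vitamin D risks or study procedures are followed for 12 months.

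Section 9 lists AE frequency and severity among the safety variables. It plans counts and percentages for all AEs and for study-related AEs. It gives no AE definition, does not mention the normal-calcium rule, and assigns no table to the noted events.

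**The concern.** Section 2 has one primary objective, the safety of the single dose. In a single-arm study of 30 children, the AE table is one of the main things a reader will use to judge it. The symptoms affected by the normal-calcium rule are the ones that Section 3 lists as acute signs of vitamin D toxicity. Vomiting after the dose is foreseen in Section 4 and asked about in Appendix A.

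Two defensible readings of the plan give two different AE tables from the same data. Under one, a child who vomits after the capsules and has a normal calcium is an AE. Under the other, that child is not an AE and cannot enter the study-related summary either, because the event is removed before relatedness is assessed. A calcium value is not a relatedness judgement: a dose can cause vomiting without raising calcium. Section 6 itself speaks of adverse events as a class that includes hypercalcemia, so the protocol does not otherwise treat the two as the same thing.

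**Working it through.** The plan states no figure on this point, so there is nothing to reproduce. The check is a comparison of text, followed by a simple scale.

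**Step 1. One event under each rule.** Take a child who vomits after the dose and whose week-1 calcium is normal.

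| Source | Result |
|---|---|
| Section 4, normal-calcium sentence | Noted in the findings, not an AE |
| Section 4, calendar footnote | AE by reference to the regulation; no calcium exception stated |
| Section 8, item 2 | AEs processed to day 30; no exception stated |
| Section 9, AE summary | Counts all AEs; does not say which rule applies |

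The regulation's text is not in the documents. What they show is that the footnote states no exception; they do not show what the regulation requires.

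**Step 2. Which calcium value decides?** The normal-calcium sentence does not say, and it orders no draw when symptoms are phoned in.

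- The calendar lists no serum calcium at screening or baseline.
- By the calendar, the week-1 draw falls at 7 ± 3 days, that is days 4 to 10.
- From that draw to the end of the 30-day window there are 30 − 10 = 20 to 30 − 4 = 26 days with no scheduled calcium, unless a raised calcium or phosphorus triggers second-tier testing ("This will include measuring a PTH with reflex calcium level as soon as possible", with repeats every 2 weeks).

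The week-1 value is the likeliest referent, but for symptoms on the dosing day or in the fourth week the plan leaves the choice to whoever completes the log.

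**Step 3. Scale.** Assume that the AE percentage is the share of the 30 enrolled children with at least one AE, and that *k* children have only the affected kind of event. The two rules then differ by *k*/30.

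- *k* = 1: 1/30 = 3.3 points
- *k* = 3: 3/30 = 10.0 points
- *k* = 6: 6/30 = 20.0 points

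The values of *k* are assumptions chosen to show a range; the documents give no rate. Under the normal-calcium rule these children contribute zero whatever *k* is, because that is what the rule says.

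**The case against.** The best defence is that a specific rule qualifies a general one. Both sit in Section 4, so Section 9's total may simply use the result. A second defence is that the normal-calcium sentence mirrors the raised-calcium one and means only that the event is not a hypercalcemia AE, leaving vomiting to the footnote. Either is possible, but they give opposite answers for the same child and the plan does not choose. Even on the first, the noted events have no place in Section 9.

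It is also fair to say that the reach is limited. The excluding sentence covers hypercalcemia-type symptoms only. Of the symptoms asked about in Appendix A, vomiting alone is named in those lists; nausea, diarrhea, constipation, gas, abdominal pain and reflux are not. The events are still recorded. Appendix A asks every child about vomiting at week 1, so ascertainment there is active. These points stand.

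A reader might go further in three ways that the documents do not support.

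- **That serious events are lost.** Section 9 describes a serious event as a kind of AE, which on a literal reading could carry the exclusion over. But the footnote and Section 8 define serious events by the regulation, and Section 8 sends safety-related events to the FDA and IRB without using the AE label as a gate. This is a wording inconsistency.
- **That late events are excluded because calcium stops.** After week 12, "No additional measures of safety, in the forms of serum calcium labs, serum phosphorus, or PTH will be measured", while AE assessments continue at weeks 26 and 52. The exclusion needs a normal calcium value, so missing calcium does not by itself remove an event.
- **That raised calcium with a single symptom goes unreported.** The raised-calcium sentence requires more than one symptom, but the footnote definition is the natural default. Section 9 reports the proportion with raised calcium, and Section 10 grades hypercalcemia by calcium alone.

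**Conclusion.** The point holds as an unresolved conflict over AE classification, and it should be fixed. Applied as written, the normal-calcium sentence lowers a safety variable that Section 9 names, and it does so before relatedness is considered. The footnote contains no such exception, and Section 9 does not settle which governs.

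The size is 3.3 percentage points for each child whose only event is of this kind, given 30 children in the denominator. The total effect is unknown because the number of such children is not given, and it may be nil.

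The consequence stops at the AE and study-related AE summaries. The primary endpoint, the estimate of the proportion with raised calcium and the accrual hold at more than 10% hypercalcemia do not depend on it. The conclusion rests on the absence of a stated exception in the footnote, not on any reading of the regulation.

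**What to change.** Reconcile the two Section 4 classification sentences, the calendar footnote and Section 9.

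1. Remove the normal-calcium exclusion from AE classification in Section 4.
2. State in Section 9 that the AE and study-related AE summaries use the single definition cited in the footnote, whatever the calcium value.
3. Report symptoms with raised calcium as a separate subset of the AE table.

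If the sponsor prefers to keep the Section 4 category, the minimum is a Section 9 sentence saying so, and a row for noted symptoms with normal calcium beside the AE table. The deciding calcium value should then be named.

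The cost is protocol wording and some extra AE log entries. AE counts will look somewhat less favourable and, with no control group, will include background illness; the study-related summary already planned in Section 9 separates that. When the subset is read, note that Section 4 describes telephone questioning about hypercalcemia symptoms only for children with raised calcium ("they will be contacted via telephone to be queried about symptoms of hypercalcemia such as muscle weakness"), so symptoms other than vomiting may be less completely reported in the rest. Visits, blood draws and clinical handling do not change.
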